#### Inclusion/Exclusion Criteria.

## Inclusion criteria are:

- (1) AA Veterans (self-identified race will be the gold standard; bi- and multi-racial included) aged 18 years or above (19 years or older in Alabama) with a diagnosis of gout (1 inpatient or ≥2 outpatient International Classification of Diseases, ninth revision, clinical modification [ICD-9-CM] codes 274.x or 274.xx)(2),
- (2) Meet the American College of Rheumatology (ACR) classification criteria for gout,(25)
- (3) Currently prescribed and filled oral ULT medication prescription (allopurinol or febuxostat) for at least 6-months.
- (4) ULT MPR < 0.80 during the run-in period; and
- (5) Able to provide informed consent.

Exclusion criteria are ULT MPR ≥0.80, current enrollment in another research study and patients who must redistribute daily pill into pillbox.

### Study advertisement and recruitment.

The study will be advertised via IRB-approved flyers at various VA bulletin boards for research studies at BVAMC and in the primary care clinic patient waiting rooms. We will also advertise through emails to the primary care physicians at regular intervals. Since we are recruiting gout patients with low medication adherence only from minority population and patients with low medication adherence have low recruitment and retention rates, we will have a three-pronged study recruitment approach for a period of 3 years.

Mailed Letter with Opt-out (Appendix 5 shows the Standard operating Procedure [SOP]). An IRB-approved invitation letter will be sent to all BVAMC and affiliated CBOC patients with a diagnosis of gout found with the help of Automated Data Package Application Coordinator (ADPAC) at BVAMC (Appendix 6). Eligible patients will be identified using an automated VINCI pharmacy query for all AA Veterans with Igout. On a weekly basis, the research assistant will receive a list of Veterans at BVAMC who filled a ULT prescription along with the dates of ULT refills in the last 6-9 months. This list will be accessible to the research assistant within VISTA. From this weekly list of potential participants, the research assistant will identify AAs with gout. Race will be preliminarily ascertained from the patient's inpatient and outpatient CPRS medical record. Letters will be mailed on a weekly or less frequent basis (based on the number of new eligible patients) and tracked using Microsoft Excel to avoid re-contacting patients.

In the mailed letter, patients will be provided with an opt-out card (**Appendix 7**) indicating that they do not wish to be contacted for the study participation. Patients who send back the opt-out card will not be contacted. The Pl/study coordinator will call (**Appendix 8-10**) eligible patients not returning the opt-out card after 14 days and complete the study screening form over the phone (confirmation of age, race/ethnicity, gout diagnosis, current adherence to gout medications, etc.) (**Appendix 10**). Patients meeting eligibility criteria will be invited to participate. The step-by-step logistics of mailing Recruitment Letters are described in **Appendix 5**. Details of how we will maintain records of patients screened and recruited are shown in **Appendix 11-12**.

Clinic Recruitment from Primary Care and Rheumatology Clinics. As a second form of recruitment, their providers will tell patients in primary care and rheumatology clinics about the study. Eligible patients will be identified from a second VISTA query of AA Veterans with low adherence to ULT who have primary care clinic visits scheduled for that week. The research associate will inform VA physicians of potentially eligible gout patients. On days when a potential research subject is scheduled for their clinic visit, the research assistant will be available. The primary care providers will inform potential research subjects of the study and ask them if they would like to participate. Those potential research subjects interested in the study will either be given a card to contact [name] or his study coordinator or speak with the research associate if available when the patient is at the BVAMC. Subjects will be screened in the clinic by filling the screening form provided by the research associate and enrolled in the study if eligible at the time of the primary care clinic visit.

Flyer Assisted Recruitment. This will be done by placing IRB-approved study flyers in the VA primary care clinics and CBOCs with the contact information for [name]/study coordinator (**Appendix 13**). Veterans interested in the study will contact the study coordinator and will be screened for eligibility either on phone or at their next visit to BVAMC. Eligible Veterans will be enrolled immediately after screening (if screened in person) or at their next visit to BVAMC (if screened on phone).

Using the 3 methods of recruitment, we have created a Study Recruitment Diagram (Appendix 3).

#### **Enrollment.**

Veterans screened on the phone will be enrolled in the study at their next clinic visit. Patients recruited in clinic will be enrolled in the study following their clinic visit. Every patient will first complete the study run-in visits, as detailed above. To enroll, patients will meet with the research associate at their regular clinic location and, once their scheduled clinical visit ends, walk to a private area for more detailed screening and enrollment. Alternatively, the patient will meet the research associate at the study clinic if they we screened on the phone and are coming for the study visit only that were scheduled with the research associate on the phone at the time of screening.

The setting for the consent process will be in a clinic room (rheumatology or primary care) or conference room 7204 in the Birmingham VA Medical Center. This room (7204) has been reserved for this activity. During the consent, we will avoid language and attitudes that could imply coercion or undue influence. [name] or a member of the research team approved to consent patients will tell interested patients about the study. Prior to beginning the informed consent process, they will confirm with the patient that they are interested in hearing more about the study. If so, then the PI and/ or a member of the research team will proceed with the informed consent process, reading through the IRB-approved consent form with the patient. After each section, they will pause to ask the patient if they have any questions. Once completed, the participant will be asked to sign the

informed consent and HIPAA documents. During the consent process, we will avoid language and attitudes that could imply coercion or undue influence. The entire consent process will be conducted in a private office behind a closed door to ensure privacy. Patients will be given up to 60 minutes to read the informed consent, discuss any question they may have with the study staff, and sign the consent. After informed consent documents are signed, copies will be immediately taken to the Research Compliance Officer at the BVAMC. The original documents will be stored in a locked file cabinet in [name] office at the BVAMC. We expect all our patients to be fluent in English and no need to have the consent translated to other languages.

## Baseline study assessments.

After the patient has been consented and enrolled in the study, they will then complete the baseline patient assessments using VA Research Electronic Data Capture (REDCap) on IPad. Paper surveys will be used as a backup. Assessments will include the following:

- (1) Demographics: age, gender, income (covariates), marital status;
- (2) Baseline frequency of gout flares requiring treatment and baseline patient satisfaction with ULT treatment;
- (3) Baseline gout-specific HRQOL assessment using the gout assessment questionnaire (GAQ);
- (4) Alcohol use and BMI (covariates; exploratory outcomes since alcohol and higher BMI are associated with higher risk of incident gout, gout flares and higher sUA level (1, 26-28));
- (5) Blood draw for baseline sUA;
- (6) ULT non-adherence on self-reported questionnaire by Voils et al.;(29) and
- (7) Self-reported ULT use from non-VA sites (non-VA ULT use; sensitivity analyses). Patients' usual care serum urate values will be captured at this visit.

Additional information will be obtained including contact information, best time to contact and email address. Veterans will be provided with \$25 remuneration (VISA gift card or VA Form 10-7078 - Participant payment voucher) for completing study assessments at the screening and baseline visit. If payment voucher is used, participant will bring this voucher to agent cashier to receive \$25 on the same day. VA CDW and inpatient/outpatient SAS files assessed through the VINCI database. Medical records databases will be used to assess comorbidity, demographics (marital status) and baseline health care utilization and ULT medication adherence for the last 6-9 months (see eligibility criteria). Patients without DVD players will be provided with a DVD player to watch the DVDs at home at 2- and 4-months.

### The consent process.

The setting for the consent process will be on the conference room 7204 or the clinic room (as preferred by the Veteran). W have reserved 7204 for this activity. We will avoid language and attitudes that could imply coercion or undue influence. [name] or a member of the research team will tell patients about the study. They will ask the patient if they are willing to participate in the study. Following a description of the study and how the data will be used, the participant will be asked to read and sign the informed consent. All of this will be conducted with the door closed. Patients will be given up to 60 minutes to read the informed consent, discuss any question they may have with the study staff, and sign the consent.

After informed consent documents are signed, those will be immediately stored in the locked study file in [name] office at the BVAMC. We expect all our patients to be fluent in English and no need to have the consent translated to other languages. All study-related data will be stored in [name] secure office at BVAMC.

#### Randomization and allocation to treatment.

Once patients complete all baseline assessments, they will be randomized into one of the two groups (see details below). Randomization will be based upon a permuted variable block design. An online computerized simple randomization scheme will be programmed by [name] (biostatistician) for BVAMC with redundant systems established to avoid interruption during periods such as server upgrades and maintenance, available through a secure Internet link. Due to the nature of interventions, patients will be aware of the group assignments. The two treatment groups are:

Group 1: Storytelling intervention

**Group 2**: Usual care (attention control)

The intervention group will receive the delivery of the storytelling video modules at baseline (in-person), study month 2 (by mail), and study month 4 (by mail). Storytelling in African-American Veterans' own voices will focus on improving ULT adherence, along with patient-narrated video segments about gout and its treatment under "Learn More", by adapting a pre-tested power-point slide presentation narrated by a Veteran with gout. Following the baseline assessment and storytelling video modules, Veterans will then complete 6 and 12-month assessments. The intervention group will also get a printed copy of the stories and the power-point presentation in the "Learn More" section at baseline. Each intervention installment will present new stories and "Learn More" gout content. Participants will be introduced to the MEMSCap and trained during their initial visit by research assistants.

The usual care comparison will be identical to the intervention condition, aside from not including the storytelling modules. The usual care group will be attention control with the same length of video segments as in the intervention group on stress management adapted from the Centers for Disease Control narrated by the same Veteran, who narrated the gout power-point presentation.

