With VA HSR&D pilot funding (PPO 14-111), we have completed the development of the storytelling intervention. The purpose of developing the Storytelling Intervention Video in the pilot study was to test it with our subsequent study, which is this fully funded HSR&D merit review. The veterans participating in the intervention video signed the HIPAA Authorization and consent for use of picture and voice. These documents stated that the video recordings will be "analyzed for effectiveness" (as stated in the video recording consent document). The proposed study is to analyze the effectiveness of the intervention video that will "disseminated to other gout patients" (as stated in both HIPAA and Video recording consent documents- **Appendix 1**-highlighted). We will determine the effectiveness of the intervention compared to usual care by conducting a 12-month multicenter randomized controlled trial (RCT) among 150 AA Veterans with gout with a ULT adherence of <0.80 at Birmingham VAMC (total 300 AA Veterans at the 3 proposed VA sites- Birmingham, St. Louis, and Philadelphia VA Medical Centers).

[figure not shown]
Our objective is to test the effectiveness of a patient-centered, culturally relevant narrative intervention, or "storytelling," based on the solid conceptual foundation of the narrative communication theory(19) and the constructs of the Health Belief Model,(20) (HBM) to improve medication adherence and outcomes in chronic diseases among African-Americans (AA), using gout as an example. Gout is a chronic disease associated with chronic symptoms and disability interrupted by intermittent acute flares, similar to Chronic Obstructive Pulmonary Disease (COPD) and Congestive Heart Failure (CHF) that leads to joint destruction if not treated appropriately. Due to the intermittently symptomatic nature of chronic conditions patients, often don't perceive disease severity and susceptibility to disease complications, and, therefore, may not balance the barriers and benefits to medication adherence.(21) Storytelling in the patients' own voice has the power to directly and more effectively confront a patient's barriers to medication adherence, reinforce the benefits and provide useful cues to action.(22) Storytelling promotes patient engagement when the patient identifies with the storyteller and can lead to a patient's recognition of the need to treat the condition and improve health outcomes, as

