Figure 1 below shows the anticipated study flow diagram for this project. The primary aims are to study the effectiveness of novel storytelling on ULT adherence and patient outcomes in gout. In Aims 1 and 2, we will conduct a multicenter, parallel 2-arm, 12-month RCT comparing the storytelling intervention to usual care in African-American Veterans with gout. Patients in the storytelling intervention group will view the designed storytelling video and the usual care group will view a presentation on stress management for the same time duration (attention control), on an iPAD in the clinic during the baseline visit. Mailed DVDs to the enrolled patients at 2- and 4-months with additional storytelling clips will reinforce messages for behavioral change received during the baseline visit through storytelling videos; mailed DVDs to the attention control group will provide more information on stress management. MEMSCap (Aprex Corp., Fremont, California), a medication bottle cap with a microprocessor that records the occurrence and date and time whenever a patient opens a vial using integrated microcircuits, will be used as a measure of primary outcome of ULT adherence.(24) It will be dispensed at baseline visit and data downloaded at 6- and 12-month in-person visit. Patients will receive the first 90-day supply in special bottles with MEMSCap and be trained at the initial visit regarding the importance of MEMSCap and not to discard it but bring it to the 3-, 6-, 9- and 12-month clinic visits.

Methods
Study Population.

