This is a prospective randomized study of AA Veterans with gout and low adherence to urate-lowering therapy (ULT), the cornerstone of gout treatment. The intervention being tested is a series of three videos shown at baseline, 2, and 4-months post-enrollment with follow up assessments completed at 3, 6, 9, and 12 months. We anticipate 150 Veterans to be enrolled from rheumatology and primary care clinics within the Birmingham VA Medical Center and its affiliated community-based outpatient clinics (CBOCs). Detailed patient recruitment plan is provided in **Appendix 2**, a flow chart (**Appendix 3**) and related details in **Appendix 4**. Data sources include administratively collected data from the electronic health record and the Corporate Data Warehouse (CDW) and inpatient/outpatient SAS files assessed through the VA informatics and Computing Infrastructure (VINCI) patient interviews, medication usage from MEMSCap, and a usual care blood draw to assess serum urate.

The storytelling intervention has been developed to be generalizable to all gout patients and thus we plan to recruit a representative sample at the Birmingham VA. Gout patients seen at referral clinics such as rheumatology are often selected for worse or more advanced disease and thus not representative of general patients with gout. Patients in primary care clinics are more representative and therefore, we plan to recruit across all Birmingham VA primary care clinics and rheumatology clinics.

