#### Outcomes.

- Primary outcome: Adherence to ULT as assessed directly with MEMSCap
- Secondary outcomes: Adherence to ULT as assessed indirectly by the following improved outcomes. These secondary outcomes will be assessed from patient surveys and by using the VA laboratory and

other relevant data collected by the CDW and inpatient/outpatient SAS files assessed through the (VINCI) database.

- a. Frequency of gout flares requiring treatment
- b. Patient satisfaction with treatment
- c. Achieving target serum urate (sUA) <6 mg/dl
- Exploratory outcomes will be assessed with surveys (HRQOL, self-reported ULT adherence, alcohol
  use) or from the VA database (BMI, healthcare utilization). Additional exploratory outcomes will focus
  on taking advantage of the detailed MEMS Caps data to examine the temporal relationships between
  medication adherence and specific research study events, e.g., the initial study visit, telephone survey,
  each DVD mailing, the 6 month research visit, and clinical events (e.g., an acute gout exacerbation or
  hospitalization).

Table 1: Summary of Primary and Secondary Outcomes and Outcome Measures to achieve SA1 and SA2			
Outcome	Assessments	Description	Clinically Meaningful Change
ULT adherence measured using MEMS*	3, 6, 9 and 12	Medication adherence to ULT measured using MEMSCap 	Absolute difference of 6% between groups representing a medium effect size of 0.40 (A smaller difference is unlikely to be meaningful)
Secondary outcomes (SA2)			
Number of Gout flares needing treatment	0, 1, 3, 6, 9 and 12	4-item patient-reported assessment of gout flare 	20% fewer patients with gout flares needing treatment
Patient Satisfaction with Medications Questionnaire (SATMED-Q)	0, 6 and 12	17-item patient-reported with six dimensions; 	Total score is between 5.9 and 13.4 and for SATMED-Q domain scores from 5.9 to 20.6, with most estimates close to 10.81
Serum urate <6 mg/dl	0 and 12	Serum urate standard biochemical assay 	20% more patients achieving target serum urate <6 mg/dl

\*Analyses of 12-month MEMS and secondary outcomes will indicate sustenance of treatment effects noted at 6-month

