The 12-month visit (end-of-study) will be in-person, similar to the baseline visit. The visit will be coordinated with a scheduled VA clinic visit, as much as possible. MEMSCap data will be downloaded and Veterans will complete a questionnaire assessing gout flares since last visit (including those requiring treatment) and patient satisfaction with treatment, as in 3-, 6- and 9-month follow-up. In addition, Veterans will be requested to get a blood draw for end-of-study sUA (secondary outcome)(32) and also complete GAQ as a gout-specific HRQOL measure and self-reported medication adherence questionnaire (exploratory outcomes). GAQ and sUA will be done only at 12-month follow-up (expected to take additional 30-minutes). Veterans unable to come to the study clinic for the 12-month visit will be offered sUA blood draw at their nearest CBOC (routine laboratory test) and the research associate will administer 12-month assessments via the phone interview.

Statistical Analysis.

- SA1: Improving ULT adherence, directly measured by using MEMS (Medication Event Monitoring System) Caps at 3, 6, 9 months (assess intervention's effect) and 12 months (assess durability of effect),
- SA2: Improving Gout flare rate, patient satisfaction and target serum urate (sUA) <6 mg/dl achievement, as indirect measures of better ULT adherence and important gout outcomes. We will also explore the effect of storytelling on health-related quality of life (HRQOL), self-reported ULT adherence, alcohol ingestion, body mass index (BMI) and gout-related inpatient and emergency room utilization.

For both Aims 1 and 2, descriptive statistics for demographics (age, race, income, marital status, time since diagnosis of gout) and clinical parameters (ULT adherence, # gout flares, satisfaction, serum urate, GAQ) will be examined. Given the two arm study design (storytelling vs. usual care), statistical procedures appropriate for two-group comparisons will be utilized to conduct crude as well as adjusted comparisons based upon the distributional nature of the outcome.

For the primary outcome of ULT adherence, an unadjusted analysis will be conducted using the two-sample ttest to compare ULT adherence across study arms at 3, 6, 9, and 12 months. Adjusted estimates of ULT adherence by study arm controlling for age, gender, income, alcohol, site, and other covariates will be conducted using ordinary least squares regression.

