Protocol for Handling Prospective Data Collection Instruments. We will use VA Research Electronic Data Capture (REDCap) within the VA Information Resource Center for all data storage and data collection for the prospective data. An enrollment and tracking system will be developed. The research coordinator and research assistant will be trained on its use. Each site will have its documents maintained on a secure shared folder. The Birmingham research coordinator will maintain a master tracking system to monitor overall study progress with recruitment goals. Preference will be for digital data collection. For in-hospital data collection, iPads with the Citrix application will be used to access the electronic data collection tools. The iPads will be set up by the local Office of Information Technology and will be encrypted prior to use by the study team personnel. We have confirmed that all participating hospitals have WIFI for remote connection. We will assist Veterans navigate through the survey on Ipad if they are not familiar with the use of Ipad technology. For follow-up phone calls, the research coordinator or research assistant will access the forms directly and complete. If REDCap access is unavailable, paper forms will be used. Once paper assessments are complete, data will be entered into an electronic database using double data entry and securely stored. All data will be protected behind VA firewall.

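### Does naming both permuted blocks and simple randomisation, for Birmingham only, leave the allocation unsound?

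*Combined protocol and SAP*

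**What the plan says.** The section on randomisation and allocation to treatment states: "Randomization will be based upon a permuted variable block design. An online computerized simple randomization scheme will be programmed by [name] (biostatistician) for BVAMC". The rest of that sentence concerns back-up systems and secure internet access. The section adds that patients will know their group. The document gives no block sizes, allocation ratio or stratification factors.

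On sites, the document speaks in two ways. The Introduction gives "total 300 AA Veterans at the 3 proposed VA sites- Birmingham, St. Louis, and Philadelphia VA Medical Centers" and says "we will conduct a multicenter, parallel 2-arm, 12-month RCT comparing the storytelling intervention to usual care". The section on handling prospective data collection instruments says "Each site will have its documents maintained on a secure shared folder". The Statistical Analysis section fits the adjusted regression for adherence "controlling for age, gender, income, alcohol, site, and other covariates". The Study Population text, however, is written for one site: "We anticipate 150 Veterans to be enrolled from rheumatology and primary care clinics within the Birmingham VA Medical Center". Recruitment and consent are likewise described for Birmingham, and the Human subjects protection section places all the research there.

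**The concern.** In standard usage, permuted blocks restrict the sequence so that the arms are equal at the end of each block, whereas simple randomisation makes each assignment independently. A programmer could build either and claim to follow the text, and no other section settles which was meant. The system is also tied to Birmingham, although the trial names St. Louis and Philadelphia too.

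Three things could be at stake:

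- **Balance.** Simple allocation can leave the arms uneven, overall or within a site, and cost precision.
- **Predictability.** Patients know their group, and staff enrol them in person. Blocks of guessable size could let staff anticipate an assignment.
- **Reporting.** The allocation method could not be described correctly from this text alone.

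**Working it through.** The plan gives no figure to reproduce here: it states no significance level, power or sample-size formula. The check is therefore how much the result depends on which method was meant.

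**Inputs from the document.** Total 300 and Birmingham 150 (Introduction and Study Population). Effect size from Table 1: "Absolute difference of 6% between groups representing a medium effect size of 0.40", so the implied standard deviation is 6/0.40 = 15 percentage points.

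**Assumptions.** Allocation 1:1 at every site, two-sided 5% level, two-sample t-test. The sizes of the other two sites are not stated, so no figure is given for them.

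**Step 1: arm sizes at Birmingham under simple randomisation.** One arm's size is X ~ Binomial(150, 0.5).

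- P(63 ≤ X ≤ 87) = 0.959, the narrowest symmetric range holding at least 95%.
- Mean absolute difference between arms: 9.76 patients.
- P(larger arm ≥ 90), that is 60:40 or worse: 0.0176.

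With a permuted-block list for the site, the difference never exceeds half the largest block. If the largest block were 8 (an illustration only), that is 4 patients.

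**Step 2: cost in precision.** The standard error relative to equal arms is √[(1/a + 1/b)/(2/75)].

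| Split | Ratio |
|---|---|
| 75:75 | 1.000 |
| 87:63 | 1.013 |
| 90:60 | 1.021 |

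**Step 3: cost in power for the whole trial.** Power comes from the noncentral t distribution with noncentrality 0.40 × √[ab/(a + b)] and a + b − 2 degrees of freedom.

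| Patients analysed | Equal arms | Averaged over Binomial(N, 0.5) |
|---|---|---|
| 300 | 93.23% | 93.15% |
| 240 | 86.99% | 86.85% |

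The second row applies the dropout of about 20% that the Patient retention section allows for: 300 × 0.80 = 240. The loss from simple allocation is 0.08 percentage points in the first row and 0.14 in the second.

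**Step 4: bias.** Under either method each patient has the same chance of each arm, so the expected difference between arms is the treatment effect. If the ratio is the same at every site, arm is not associated with site in expectation, whether there is one list or three. Chance imbalance within sites is handled in the adjusted regression, which already includes site.

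**Step 5: the two sentences side by side.** The first says what the allocation is based on and names a technical design. The second says who programs the tool, how it is reached and how it is kept running. A named design is unlikely to be withdrawn by one adjective in a sentence about software and server maintenance.

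**The case for a change.** The best case for a change is that these are established technical terms in the one section where they matter, that the contradiction lies in adjacent sentences, and that one or two sentences would remove it. The Birmingham focus does not fully excuse the silence on the other sites, because the same document contains the multi-site analysis plan. Patients know their group, so the method also affects how predictable the next assignment is.

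The textual part stands: the wording is inconsistent, and the reader is not told how patients at St. Louis and Philadelphia are allocated. It does not show that any result would differ. The site question is not peculiar to randomisation either, since recruitment and consent are also described for Birmingham.

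Predictability cuts the other way. Simple allocation is the less predictable method, and blocks are the ones that need protection, which varying their size partly supplies. Prescribing a separate blocked list for each site would therefore be a new design choice. The document promises no stratification by site. The gain would be about 2% in standard error for a split with probability below 0.02, set against somewhat greater predictability.

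**Conclusion.** No change to the plan follows. The passage contains a probable clerical slip (one loose adjective) and a site reference that fits a document written largely for Birmingham. Under either reading the comparison is unbiased, and power differs by less than 0.2 percentage points with 300 or 240 patients analysed. At Birmingham the standard error rises by 1.3% at the edge of the 95% range and by 2.1% at 90:60. These figures assume 1:1 allocation at all sites, a two-sided 5% level and the plan's effect size of 0.40. The 93% power is for comparing the two methods without dropout and should not be quoted as the trial's power.

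The gap is one that the trial statistician fills from the randomisation program itself: the report names the method that was used and the sites it covered. Separate lists by site remain an option for the sponsor and do not correct an error.
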